4.3.7.2. Data from Literature

Reports in the literature suggest that viral dynamics are correlated to risk of mortality for AdV; AdV infection has been established as an independent risk factor for death (Hiwarkar 2013,

Lion 2010, Mynarek 2014, Symeonidis 2007). Overall survival was associated with lowest peak AdV viremia levels; patients with peak AdV viremia < 1000 copies/mL had an overall survival similar to AdV viremia-negative patients (Mynarek 2014). In this same study, patients with peak AdV viremia levels > 10,000 copies/mL had poorer survival (hazard ratio=3.81; p=0.003). Hiwarkar and colleagues demonstrated in a retrospective cohort of 291 high-risk children (years 2005 to 2010) that AdV viremia was a major independent predictor of mortality (p < 0.05) (Hiwarkar 2013). In this cohort, AdV reactivation caused prolonged hospitalization (p < 0.05) and accounted for 15% of all mortality. Recently, Hiwarkar and colleagues have shown that death from disseminated adenoviral disease may be associated with failure to respond to therapy, as measured by cumulative viral load despite treatment with IV CDV (Hiwarkar 2017).

Ongoing work at the Royal Manchester Children’s Hospital in the UK to explore the impact of AdV viremia upon outcomes has shown the clear impact of increasing AdV viremia (in spite of the application of pre-emptive IV CDV therapy) on increasing mortality (Figure 5).

Figure 5: Relationship between AdV Viremia and Mortality (Viremia Modelled as Time-varying Covariate)

[figure not shown]
Source: [name], Royal Manchester Children’s Hospital, unpublished data.

Each point (“+”) on the plot represents an individual viral load measurement, plotted against its Martingale residual (i.e., “excess mortality”), which is defined as observed mortality minus expected mortality. Observed mortality is “0” for censored observations (i.e., alive at next measurement or censored prior to next measurement) and “1” for events (i.e., dead prior to next measurement or censored). Expected mortality is the integrated hazard obtained from a Cox

model with viral load included as a time-varying covariate. A non-parametric smoothing line is used to show the relationship.

Figure 6 represents a similar analysis using viremia at the time of initial diagnosis of significant AdV. While the trend is less clear, even with this small sample size, there is still evidence to suggest that higher viremia is associated with higher mortality.

Figure 6: Relationship between Baseline Viral Load and Mortality (Viral Load as Time of Initial Viremia > 1000 copies/mL)

Source: [name], Royal Manchester Children's Hospital, unpublished data.

4.3.8. Rationale for Limiting Access to BCV for SoC Subjects to after Week 16 Post-randomization

While a BCV crossover option for subjects who fail to respond to SoC therapy would be expected to have support from physicians who have used BCV for IV CDV failures via the NPP, subjects who are randomized to the SoC arm in this study must remain in their assigned treatment arm without the option for BCV treatment through a minimum of Week 16 post-randomization to allow for a meaningful and interpretable comparison of safety and efficacy between the treatment arms. The aim of this study is to show a positive risk-benefit for BCV when compared with SoC-based preemptive therapy for AdV viremia in pediatric HCT recipients. This will only be possible if SoC-treated subjects are not allowed to switch to BCV in the event of failure during the 16-week virologic response-driven treatment period. Crossover in a substantial proportion of SoC-treated patients has the potential to negatively impact interpretation of the planned efficacy comparisons for BCV vs. SoC by decreasing the sample size available in the SoC arm after the switch for several of the secondary efficacy endpoints, including time to clearance of AdV viremia and sustained virologic response. Similarly, early

switching could also potentially complicate interpretation of the safety and tolerability assessments of BCV vs. SoC. Attribution of events such as SAEs and all-cause and non-relapse mortality in this complicated post-HCT patient population could also be more difficult. There would also be the potential for significant differences in the duration of BCV vs. antiviral exposure in the SoC arm and follow-up times.

4.3.9. PELOD Scoring

Because the pathogenesis of AdV infection is related to lysis of cells in key organs, such as the lungs, liver and gut (and viral load in plasma is thought to reflect the extent of cellular lysis, supported by correlations between peak viral load and mortality; [Heim 2011](#)), capturing decreased viral burden (as viral AAUC) is highly likely to correlate with decreased organ damage. Maximum pediatric logistic organ dysfunction (PELOD) score has been added as a validated surrogate outcome measure for severely-ill pediatric ICU patients ([Leteurtre 2003](#)). It quantifies the degree of dysfunction across several organ systems (neurologic, cardiovascular, renal, respiratory, hematologic, and hepatic) and has been shown to correlate with mortality in pediatric HCT recipients ([Balit 2016](#)), thus offering an opportunity to quantify the effect of BCV vs. SoC in limiting the occurrence of organ dysfunction by AdV infection.

[figure not shown]
4.3.10. Exploratory Biomarker Analyses

Because early detection of BCV-related GI AEs could allow early intervention, several exploratory biomarkers are proposed for potential use in these patients, including citrulline as a marker of GI toxicity ([van der Velden 2010](#)), suppression of tumorigenicity-2 (ST2) and T cell immunoglobulin mucin-3 (TIM3) as markers of GVHD ([McDonald 2015](#)), and C-reactive protein (CRP) concentrations as a non-specific marker of inflammation ([Clyne 1999](#)). Because of the unknown effect of BCV on these markers, they are considered exploratory. Analysis of these biomarkers may support their use in future clinical studies of BCV.

4.4. Benefit:Risk Assessment

There is no approved therapy for the treatment of AdV infection. The current SoC may include reducing immunosuppression or off-label use of IV CDV; ribavirin is not recommended by ECIL and is rarely used. The efficacy of IV CDV for the treatment of AdV viremia in HCT recipients has not been formally established, with some reports in the literature describing high success rates in controlling viremia and others describing very poor response rates ([Ganapathi 2016](#), [Lion 2014](#)). The ECIL Treatment Guidelines note that while pre-emptive treatment of AdV with CDV has been reported in several studies, the “evidence concerning the effectiveness on mortality is inconsistent,” with AdV-related mortality rates varying from 23% to 50% despite pre-emptive treatment, and an AdV-related mortality of 18% has been reported for patients not receiving pre-emptive therapy ([Matthes-Martin 2012](#)).

Hiwarkar and colleagues have recently reported their experience with oral BCV, obtained via the NPP ([Hiwarkar 2017](#)). They compared virologic response amongst BCV recipients (generally applied in the setting of IV CDV contraindications or failure of IV CDV therapy) vs. those that were treated with IV CDV, as shown in [Figure 7](#).

Figure 7: Virologic Responses after BCV or CDV Treatment in Pediatric HCT Recipients

[figure not shown]
Abbreviations: ADV = adenovirus.
Source: [Hiwarkar 2017](#).

Rapid virologic response in pediatric HCT recipients (defined by the authors as $\geq 2 \log_{10}$ copies/mL decline in AdV viremia at two weeks) was more common with oral BCV (13/18, 72%) when compared with IV CDV (2/23, 9%). Patients were treated until viremia cleared; the median time to clearance of viremia with BCV was 4 weeks (range: 2 to 9 weeks) compared with 9 weeks (range: 3 to 15 weeks) with IV CDV ($p < 0.005$). The rapid antiviral response reported in these cohorts is consistent with the responses observed in interventional clinical trials with BCV (see Section 4.3.7 and the BCV Investigator's Brochure for more details). Furthermore, the lymphocyte count at the time of resolution of viremia was lower in patients receiving BCV than for those who received CDV. It is also noteworthy that many of the BCV patients had previously failed CDV.

[Figure 8](#) shows the lymphocyte count at the resolution of viremia with BCV ($n = 15$) and CDV ($n = 8$). The median lymphocyte count at the resolution of viremia after BCV was 320 cells/ μL and after CDV was 910 cells/ μL . Thus, the resolution of viremia occurred in the BCV group

despite significant lymphopenia, while resolution of viremia occurred in the CDV group when lymphocyte count was $> 300/\mu\text{L}$ ($p < 0.05$). The academic consortium also concluded that BCV was generally well tolerated: only 1 of 18 patients temporarily interrupted oral BCV for GI AEs, while renal toxicity was observed in 9 of 23 patients treated with IV CDV. The lower GI toxicity may in part be attributable to the shorter courses of BCV therapy used in these cohorts.

Figure 8: Lymphocyte Count at Resolution of Viremia Following Treatment with BCV (n = 15) or CDV (n = 8)

Abbreviations: BCV = brincidofovir; CDV = cidofovir.
Source: [Hiwarkar 2017](#).

The primary risk associated with IV CDV is nephrotoxicity, which can result in renal failure or death ([De Clercq 2003](#), [Safrin 1997](#), [Vistide Package Insert \[Gilead Sciences 2010\]](#)). This is of particular concern for HCT recipients who are at increased risk of acute renal injury during the first 100 days post-transplant, with doubling of serum creatinine values reported in 15% to 73% of HCT recipients, and renal failure requiring dialysis in up to 8.5% of HCT recipients ([Hingorani 2005](#), [Rajpal 2013](#)).

Cohort studies have shown that kidney injury is associated with poorer prognosis and mortality in pediatric HCT patients ([Bhadri 2009](#), [Ljungman 2003](#), [Vora 2015](#)). One retrospective cohort of pediatric patients who received IV CDV for the treatment of AdV demonstrated significant association of acute kidney injury (defined as ≥ 0.3 mg/dL [SI: ≥ 27 $\mu\text{mol/L}$] increase in serum creatinine) and mortality. All 6 subjects who met this threshold died, whereas, all 17 subjects who did not meet this threshold survived ([Vora 2015](#)).

The primary clinical risks associated with BCV therapy are GI in nature, particularly diarrhea, and elevations in serum aminotransferases. The emergence of diarrhea in the early post-HCT period is problematic due to mimicry of the symptoms of GI GVHD ([Detweiler 2016](#), [Marty 2016](#)), which led to a significantly higher use of immunosuppressants on the BCV arm that resulted in poor outcomes in Study CMX001-301. Based on clinical trial experience to-date, the monitoring and management stopping rules for BCV therapy have been refined to include

clear and mandated thresholds at which BCV should be temporarily withheld and when BCV should be permanently discontinued, regardless of the suspected etiology of the diarrhea (see Section 8.3.2). Further, a response-driven approach to shorten BCV treatment duration, supported by the early and rapid antiviral response observed with BCV treatment, will be assessed to minimize exposure and the risk of BCV toxicity by treating until AdV viremia is cleared (see Section 8.3).

Safe and effective therapy for treatment of AdV is currently not available. The BCV response-driven treatment strategy, combined with clear and definitive toxicity management guidelines, informed by clinical trial and cohort data available to-date, are intended to maximize potential benefit to subjects, while decreasing the risk. As a result, the benefit:risk profile is considered sufficiently favorable for the continued assessment of oral BCV in pediatric recipients of T cell-depleted allogeneic HCT with AdV viremia. A DSMB will be chartered to evaluate the PK, safety, tolerability, and mortality data by treatment arm on an ongoing basis throughout the conduct of the trial (Section 4.5).

All sites will be encouraged to enroll their subjects in the “Chimerix Registry for BCV” (Study CMX001-333: A Prospective Observational Study for the Long-term Follow-up of Subjects Previously Enrolled in Selected Clinical Studies of BCV) to assess the long-term impact of exposure to BCV. Both BCV and SoC recipients will be invited to participate, with the latter serving as a control group for the BCV treated group.

More detailed information about the known and expected benefits and risks of BCV, including the Reference Safety Information, is provided in the BCV Investigator’s Brochure.

4.5. Independent Safety Oversight

4.5.1. Data and Safety Monitoring Board

A DSMB will be convened according to US Food and Drug Administration (FDA) and European Medicines Agency (EMA) guidelines on clinical trial data monitoring committees to monitor safety for this study. The DSMB will review safety data on an ongoing and scheduled basis, as determined by the board and detailed in the DSMB charter. The DSMB Chair will be allowed to convene ad hoc meetings, as necessary, and meetings may be convened more frequently if unexpected safety issues arise.

The DSMB will define specific safety information to be provided for review at each meeting, but the DSMB review package will minimally include:

- All SAEs
- CTCAE Grade 3 or higher AEs
- AEs resulting in permanent BCV or other anti-AdV drug discontinuation
- AEs requiring BCV or other anti-AdV drug interruption
- AEs requiring dose modification or consolidation of BCV or other anti-AdV drug
- Incidence of and time to all-cause mortality and non-relapse mortality

- Laboratory parameters predictive of liver abnormalities (e.g., ALT, aspartate aminotransferase [AST], alkaline phosphatase, prothrombin time-international normalized ratio [PT-INR], and total and direct bilirubin), renal abnormalities (creatinine clearance, eGFR), and hematologic cell counts predictive of graft function
- Observed plasma BCV concentrations (as available)

At least two safety reviews will be conducted by the DSMB. The first safety review will be performed after the first 30 subjects enrolled into the study have completed through Week 16 (or have died or are lost to follow-up). The second safety review will be performed after the first 60 subjects enrolled have completed through Week 16 (or have died or are lost to follow-up).

The DSMB Chair will receive copies of all expedited safety reports issued for BCV at the same time these reports are submitted to investigators, and may decide to convene ad hoc DSMB meetings based on these expedited reports. If the DSMB recommends changes to the study design, including changes to the protocol dosing regimens because of safety issues, regulatory authorities will be consulted, as appropriate, prior to implementation.

4.5.2. Endpoint Adjudication Committee

A blinded endpoint adjudication committee (EAC) will be convened to provide an independent assessment of whether the deaths in the study are attributable to AdV. The EAC will adjudicate all deaths following procedures defined in the EAC charter. The EAC will comprise at least two members who are experts in the field of AdV infection and/or HCT and not otherwise involved in the study.

5. STUDY OBJECTIVES AND OUTCOME MEASURES

5.1. Primary Objective and Primary Efficacy Endpoint

The primary objective of this study is to compare the safety, overall tolerability, and virologic response of BCV vs. SoC for the treatment of AdV infection in high-risk pediatric allogeneic HCT recipients. A virologic response-driven approach to the duration of treatment will be evaluated, in which subjects randomized to BCV therapy are treated until AdV viremia is confirmed as undetectable or until a maximum of 16 weeks of therapy, whichever occurs first. The primary efficacy endpoint is the AAUC for AdV viremia (\log_{10} copies/mL) from randomization through Week 16 post-randomization.

5.2. Secondary and Exploratory Objectives

5.2.1. Secondary Objectives:

- To assess the incidence of and time to all-cause, non-relapse, and AdV-associated mortality in pediatric subjects treated with BCV vs. SoC
- To assess the correlation between virologic response and clinical outcome
- To describe the incidence of and time to virologic relapse in subjects who have previously achieved undetectable AdV viremia
- To assess resolution or progression in clinical symptoms associated with AdV disease (i.e., resolution of all disease to no disease among subjects with probable or definitive AdV disease at baseline and progression from no disease to any probable or definitive AdV disease among asymptomatic subjects at baseline)
- To assess the correlation between AdV hexon “serotype,” virologic response, and clinical outcome
- To evaluate the emergence of viral resistance among subjects treated with BCV vs. SoC
- To characterize plasma BCV PK profiles and evaluate the impact of covariates of interest on PK
- To characterize the potential impact of plasma BCV exposure on clinical safety, virologic, and mortality endpoints, and to evaluate the modifying influence of various covariates of interest on these relationships and endpoints
- To assess virologic response in other non-plasma biologic compartments (urine, stool, respiratory secretions), as well as the association between detectable AdV viral load in these compartments at AdV viremia clearance with subsequent AdV viremia relapse

5.2.2. Exploratory Objectives

- To assess the correlation between baseline HCT co-morbidity index and clinical outcome
- To assess immunologic predictors of virologic response (all subjects) and relapse (among subjects with confirmed AdV clearance from plasma)

- To evaluate exploratory biomarkers for BCV-related GI toxicity (e.g., citrulline, ST2, TIM3, and C-reactive protein)
- To assess healthcare resource utilization

5.3. Secondary and Exploratory Endpoints

5.3.1. Key Secondary Efficacy Endpoint

The key secondary efficacy endpoint is the incidence of all-cause mortality through Week 16.

5.3.2. Other Secondary Efficacy Endpoints

- Time to all-cause mortality through Week 16
- Incidence of and time to all-cause mortality through Week 36
- Incidence of and time to non-relapse mortality through Weeks 16 and 36
- Incidence of and time to AdV-associated mortality through Weeks 16 and 36, where mortality is assessed by a blinded EAC
- Proportion of subjects with undetectable AdV viremia at Weeks 2, 4, 6, 12, and 16
- Proportion of subjects with $\geq 2\text{-log}_{10}$ decline from baseline or undetectable AdV viremia at Weeks 2, 4, 6, 12, and 16
- Proportion of subjects with $\geq 1\text{-log}_{10}$ decline from baseline or undetectable AdV viremia at Weeks 2, 4, 6, 12, and 16
- AAUC at Weeks 2, 4, 6, and 12
- Incidence of and time to first confirmed undetectable AdV viremia
- Incidence of and time to virologic relapse (subsequent confirmed AdV viremia ≥ 1000 copies/mL) among subjects with confirmed clearance of AdV from plasma (overall; by AdV in urine, stool, and respiratory secretions at the time of first undetectable AdV viremia; and by T cell-mediated immune function [e.g., CD4+ cells $>$ or ≤ 50 cells/ μL] at the time of first undetectable AdV viremia)
- Maximum PELOD score through Week 16
- Number of days spent in the hospital through Week 16
- Number of days spent in the ICU through Week 16
- Emergence of AdV mutations associated with genotypic resistance and phenotypic resistance (the latter when possible) to BCV or CDV
- Incidence of and time to progression to probable or definitive AdV disease (among asymptomatic subjects at baseline)
- Incidence of and time to resolution of AdV clinical disease (among subjects with probable or definitive AdV disease at baseline)

- Primary model-based PK parameters, such as apparent clearance (CL/F), intercompartmental clearance (Q/F), volume of central compartment (V_c/F), volume of peripheral compartment (V_p/F), absorption rate constant (K_a), and lag time (T_{lag}), secondary PK parameters, such as C_{max} and area under the plasma concentration time curve at steady state (AUC_{ss}), and identification of covariates that influence these PK parameters
- Relationship between plasma BCV exposure, other covariates of interest, and
 - safety endpoints, including GI AEs, diarrhea, ALT, total bilirubin, and other safety events of interest
 - virologic endpoints including AAUC, AAUCMB, viral load change from baseline, and other virologic endpoints of interest,
 - all-cause and non-relapse mortality through Week 16

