12.4.2. Secondary Efficacy Endpoints

Continuous secondary efficacy analyses will use the same method used for the primary analysis.

Dichotomous secondary efficacy analyses will be analyzed using a Cochran-Mantel-Haenszel test stratified by each of the stratification factors. Number of failures and failure rates will be presented for each treatment arm. Cochran-Mantel-Haenszel p-values, estimated common odds ratios, and corresponding approximate 95% CIs will be presented for each comparison. The Breslow-Day test will be used to test the homogeneity of the odds ratios. Missing data will be imputed as failure.

Most time-to-event analyses will be performed using Kaplan-Meier methods/plots and Cox models. P-values and hazard ratios along with their 95% CIs will be presented for each treatment comparison. Missing data will be censored, generally at the earlier of the end of study for each subject or the time point for the specific analysis.

Non-relapse mortality will be analyzed with relapse as a competing risk adjusted for baseline strata, with corresponding cumulative incidence plots, Fine-Gray models, and cause-specific and sub-distribution hazard ratios with corresponding 95% CIs.

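### Virologic relapse is defined only among children who cleared after randomisation, yet the general analysis rules would give it between-arm p-values and hazard ratios that are likely biased against brincidofovir

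*Combined protocol and SAP*

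**What the plan says.** - **Endpoint.** Section 5.3.2 defines relapse as later confirmed viremia of at least 1000 copies/mL "among subjects with confirmed clearance of AdV from plasma". It is to be shown overall, by virus in other compartments, and "by T cell-mediated immune function" (for example CD4+ above, or at or below, 50 cells/µL) at the first undetectable result.
- **Objective.** Section 5.2.1 words it as "To describe the incidence of and time to virologic relapse in subjects who have previously achieved undetectable AdV viremia". No arm comparison is named, whereas the mortality and resistance objectives in the same list do name BCV against SoC.
- **Analysis.** In Section 12.4.2, for dichotomous secondary endpoints, "Cochran-Mantel-Haenszel p-values, estimated common odds ratios, and corresponding approximate 95% CIs will be presented for each comparison". For times to event, "Most time-to-event analyses will be performed using Kaplan-Meier methods/plots and Cox models", and "P-values and hazard ratios along with their 95% CIs will be presented for each treatment comparison". Relapse is not exempted, and nothing addresses selection into the clearer subset.
- **Immune status at clearance.** Section 4.4 cites a cohort in which "The median lymphocyte count at the resolution of viremia after BCV was 320" cells/µL (n = 15), against 910 after intravenous cidofovir (n = 8); it adds that "resolution of viremia occurred in the CDV group when lymphocyte count was" above 300/µL. Median time to clearance was 4 against 9 weeks.
- **Link to relapse.** The Synopsis (Duration of Treatment/Study) ties recurrence of viremia to insufficient immune reconstitution. Section 4.3.2 says that cidofovir is reportedly less effective without T cell recovery.

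**The concern.** Randomisation balances the arms at Day 1. It does not balance those who later clear. If SoC mostly clears children whose immunity is returning, while BCV also clears children whose immunity is not, the BCV clearers carry more relapse risk whatever BCV does afterwards. A hazard ratio above 1 could then be read as harm from stopping BCV at confirmed clearance, which is the treatment strategy the trial evaluates. Conversely, a true relapse problem could be dismissed as selection. The planned comparison cannot separate the two readings. The Cochran-Mantel-Haenszel strata are baseline factors and cannot restore a balance lost by conditioning on clearance.

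**Working it through.** **1. The plan's own figures.** The documents give no event count, relapse rate or power for relapse. The only anchor is the primary endpoint, which confirms the design inputs (Section 12.1 and Synopsis: 94 against 47, difference 0.6, SD 1.03; two-sided alpha 0.05 assumed): Φ(0.6 / [1.03 × √(1/94 + 1/47)] − 1.96) = Φ(3.26 − 1.96) = 0.903, matching the stated power above 90%.

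**2. Expected relapse among clearers with no drug effect on relapse.** All rates here are assumptions. Half the children are immune-recovered. Let c₁ and c₀ be the clearance probabilities in recovered and non-recovered children, and r₁ and r₀ the relapse probabilities, the same in both arms. Then

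relapse among clearers = (0.5·c₁·r₁ + 0.5·c₀·r₀) / (0.5·c₁ + 0.5·c₀).

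Worked case (strong selection), with BCV c = 0.85/0.80, SoC c = 0.60/0.10 and r = 0.10/0.40:
- BCV: (0.0425 + 0.16) / 0.825 = 24.5%
- SoC: (0.03 + 0.02) / 0.35 = 14.3%

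The recovered share among clearers is 0.85/1.65 = 52% on BCV and 0.60/0.70 = 86% on SoC. That imbalance produces the whole gap.

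Simulating 3,000 trials of 94 against 47 per scenario, with a Cox model among clearers, gave:

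| Scenario (no true effect on relapse) | Clearers, BCV / SoC | Relapse, BCV / SoC | Median HR | Rejection at 5% |
|---|---|---|---|---|
| Clearance unrelated to immunity (0.80 / 0.50), r 0.10/0.40 | 75 / 24 | 25% / 25% | 1.02 | 4.8% |
| Mild selection (0.85/0.75; 0.60/0.30), r 0.10/0.40 | 75 / 21 | 24.1% / 20.0% | 1.27 | 5.0% |
| Strong selection, r 0.20/0.40 | 78 / 16 | 29.7% / 22.9% | 1.38 | 5.9% |
| Strong selection, r 0.10/0.40 | 78 / 16 | 24.5% / 14.3% | 1.88 | 8.6% |
| Strong selection, r 0.10/0.60 | 78 / 16 | 34.2% / 17.1% | 2.29 | 20% |

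With so few SoC clearers, the distortion shows mainly in the estimate and less in the false-positive rate.

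**3. A second model, in continuous time.** Recovery rate r = 1/12 per week; drug-driven clearance rate d = ln 2/4 on BCV and 1/20 on SoC; relapse hazard h = 0.06 per week after drug-driven clearance until recovery; T = 16 weeks. With a = d + r and b = h + r, the probability of clearing is 1 − e^(−aT), and the probability of clearing and then relapsing is

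(d·h/b) × {(1 − e^(−aT))/a − e^(−bT)·(1 − e^(−(a−b)T))/(a−b)}.

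- BCV: 98.4% clear and 22.4% relapse, so 22.8% of clearers relapse and 76.0% of all randomised are cleared without relapse.
- SoC: 88.2% and 10.2%, so 11.5% of clearers and 78.0% of all randomised.

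Part of this incidence gap is longer time at risk after earlier clearance. Per unit of time at risk, the null relapse rate ratio is about 1.8. With mean recovery of 26 or 52 weeks it is about 1.5 or 1.3.

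**4. Does the CD4+ breakdown solve it?** In the two strong-selection scenarios with r₁ = 0.10, stratifying the Cox model on a perfectly measured immune state returned HR 1.00 to 1.02. With 20% misclassification the HR stayed at 1.62 to 1.88. A single cut-point shown as a breakdown is not even that adjustment.

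**5. The all-randomised alternative.** Cleared without relapse = 0.5·c₁(1 − r₁) + 0.5·c₀(1 − r₀). For the worked case, BCV is 0.3825 + 0.24 = 62% and SoC is 0.27 + 0.03 = 30% (power 96%). With r₀ = 0.60 it is 54% against 29% (82%), and under mild selection 61% against 36% (80%). These omit deaths, so they illustrate feasibility only.

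**The case against.** The strongest reply is that the plan already holds most of what is needed.

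- **All-randomised measures exist.** Section 12.4.1 plans time below the detection limit and time below 1000 copies/mL, with children who die counted as above the limit afterwards. Section 5.3.2 has the proportion undetectable at Weeks 12 and 16, in the ITT set with missing data as failure. The primary viremia endpoint also rises with a rebound. This stands: a reader might infer that the plan has no randomised measure of durability, and that would be wrong. What is missing is a sustained-clearance proportion. A child who relapses, restarts BCV under Section 8.4 and is undetectable again at Week 16 counts the same as one who never relapsed. Section 4.3.8 mentions sustained virologic response as a secondary endpoint, but Section 5.3.2 lists none.
- **The test is inferred.** The objective is descriptive, Section 12.4.2 covers most rather than all time-to-event analyses, and Section 12 leaves detail to the SAP. This stands in part: it makes the plan ambiguous, but the rule as written does not exclude relapse.
- **Immune status was anticipated.** The CD4+ breakdown, and the objective in Section 5.2.2 on immunologic predictors of relapse, show this. It stands as a display, not as an adjustment.
- **The supporting data are thin.** The cohort had 15 and 8 patients and was not randomised. BCV was generally given after cidofovir failure or contraindication, and SoC here need not be cidofovir. A reader might take the lymphocyte counts as proof that clearers will differ by arm. They support a direction only.

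**Conclusion.** The point holds as a limited one. Following Section 12.4.2 as written would attach inference to a comparison that randomisation does not protect, and the protocol's own rationale suggests a bias against BCV. The size is not computable from the documents: the ratios of about 1.3 to 2.3 rest on assumed clearance, relapse and recovery rates and an assumed common relapse risk in both arms.

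Three stronger readings are not supported:

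- **That a spurious significant result is likely.** Rejection was 5.0% to 8.6% in three of the four selection scenarios and reached 20% only in the most extreme.
- **That a doubling of relapse is to be expected, with equal sustained clearance.** The continuous-time model behind 22.8% against 11.5% has no deaths, although Section 12.4.1 expects 16% to 24% by Week 16. It clears SoC faster than the cited cohort, and its 12-week recovery is shorter than the many months in Section 4.3.2. With recovery at 26 or 52 weeks, cleared-without-relapse becomes 65% against 61%, or 58% against 49%.
- **That the trial's main conclusions are at risk.** Relapse is one of many other secondary endpoints and feeds neither the primary viremia analysis nor the mortality analyses.

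**What to change.** 1. State in Section 12.4.2 that relapse among clearers is reported descriptively by arm, as cumulative incidence with death as a competing event and a stated time origin, overall and by CD4+ at first undetectable result, with no p-value, odds ratio or hazard ratio for the arm contrast. This also brings the analysis into line with the objective in Section 5.2.1.
2. Add one ITT endpoint to Section 5.3.2 and use it for the between-arm comparison: alive, confirmed undetectable, and no subsequent confirmed viremia of 1000 copies/mL or more through Week 16.
3. Present it alongside the time-below-detection-limit and time-below-1000 analyses already in Section 12.4.1. No new time-in-state endpoint is needed.

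The cost is one derived variable from weekly central-laboratory results and vital status already collected, plus a few sentences. The loss is a p-value for relapse conditional on clearance. The new endpoint answers a different question, since it mixes clearing, staying clear and surviving; the descriptive relapse display should therefore be kept beside it.
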